Descriptive statistics: Descriptive statistics, including percentage and means with 95% confidence intervals, will be used to quantify sample characteristics of the participating wards and participants. To investigate potential bias in characteristics due to self-selection, characteristics for participants and the source population will be compared for each participating wards. We will further quantify bias by calculating the ratio of proportions for categorical data and difference in means for continuous data. *Analytical statistics:* For investigating the effects of PASC on surgery-related complications, we will use binary logistic regression models using the control period as reference category. Correlation between outcomes on the same hospital (ICC) will be considered by including a random intercept for the hospitals

in the various models (exchangeable correlation assumed). To account for potential temporal trends in the outcome, we will include calendar month as a continuous (linear or nonlinear) term in all models. Additional adjustment would be required if selection bias is present.

Variables are gender (0/1), age (in years), comorbidity (ASA-classification 1-5), type of anesthesia (general, spinal/regional, or combination – nominal scores), type of surgery (nominal scores), length of surgery (knife-time in minutes/hours), type of hospital (nominal scores), and month of surgery (1-27). Outcome variables: complication (one or more) up to 30 days after surgery, readmission to hospital within 30 days, mortality up to 30 days after surgery, and length of hospital stay.

Non-response and selection bias

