Preliminary data collection suggests that the participation rate for PASC is 50% (Harris et al, 2022). If participation probability is associated with characteristics that also are related to the outcome under study, effects of PASC on surgery-related complications could be biased. In the table example below, the risk of complication in complete data with no self-selection would be 15% and 10% for the control and intervention periods, respectively. With 50% non-response (and strong selection on characteristics) in the intervention period, the corresponding risk of complication could be only 5%. Thus, a large risk reduction in the intervention period could be ascribed selection rather than the intervention. Fortunately, our study is prospective in that the outcome is measured after the intervention take place. Accordingly, only the difference in patient characteristics between control and intervention period can affect the difference in future outcome. Following this, regression adjustment for difference in patient characteristics would probably be sufficient to adjust for selection bias (1).

Protocol deviation and intention to treat (ITT)

Protocol violations for the PASC intervention may include incomplete response to questionnaire, not operated after all, or other aspects that might imply that the patients should not be included for analyses. In such cases, we will still include subjects as if they had been treated (intention to treat analyses). If we were to exclude patients due to protocol violation (per protocol analysis), this could lead to serious bias which is not possible to correct using adjusted regression analyses.

This description of statistical analysis and power analysis was performed by biostatistician and [name] [name] in collaboration with [name] [name], in the updated 2.0 version of the protocol.

Reference

- Harris et al. Development and validation of patients' surgical safety checklist. BMC Health Services Research. 2022; 22:259.
- Harris et al. Feasibility of implementing a surgical patient safety checklist: prospective cross-sectional evaluation. Pilot and Feasibility Studies (2023) 9:52
- Storesund A, et al. Clinical Efficacy of Combined Surgical Patient Safety System and the World Health Organization's Checklists in Surgery - A Nonrandomized Clinical Trial. JAMA Surgery. 2020;155(7):562-570.

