Statistical analysis plan b) on the PASC checklist on patients self-screening on their risk of malnutrition prior to surgery.

The main hypothesis is that PASC reduce the risk of nutritional events after surgery. Nutritional complications are a primary outcome based on ICD-10 codes, and secondary outcome are comparison of patients and healthcare staffs' risk assessments by comparing use of the Malnutrition Screening Tool (MST) (Ferguson et al, 1999). Three MST items are scored from 0-7, where a total sum score at 2 and above, represents patients being at risk of malnutrition. Secondary hypothesis is that patients can screen themselves of the malnutrition risks and just as well as the healthcare staffs' screening of the patients' malnutrition risks.

Descriptive analysis with frequencies, percentages, means, and standard deviations will be applied. A chi-squared test will be applied to detect differences in patient characteristics and clinical variables from baseline to intervention steps. A logistic regression model will be used to adjust for any variations in characteristics or clinical variables between control and intervention steps. Validity of the Malnutrition Screening Tool will be investigated with nutrition parameters of the scale and objective variables (ICD-10 codes). Agreement between patients' ratings and healthcare staffs' ratings on the malnutrition risk scale will be measured with percentages, Kappa and intraclass correlation (ICC) with absolute agreement as appropriate. Correlations will be performed with Pearsons' correlation or Spearman's rho, as appropriate.

Missing data will be managed by creating 200 imputed datasets and the imputation model included all variables to be included in adjusted regression model. Statistical analyses will be performed by Stata and in SPSS. All P-values are two sided and values $P < 0.05$ are considered statistically significant.

The statistical analysis plan was described in the protocol 1.0, 2.0 and 2.1, and further detailed here, by [name] [name].

Reference

Ferguson M, et al. Development of a Valid and Reliable Malnutrition Screening Tool for adult Acute Hospital Patients. *Applied Nutritional Investigation*. 1999; 15(6):458-464.

Statistical analysis plan for parts of both a) and c)

Statistical analysis plan for the Patient Safety Checklist Experience Questionnaire (PASC-EQ) and the PASC Implementation Questionnaire (PASC-IQ)

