The statistical power of the PASC trial is based on sample size calculations referred to in the protocol and in the Statistical Analysis Plan for the trial, where 2660 in each arm with a total of 5320 cases would be required to detect a 5% reduction of events. The clinical data from the trial and health economic data such as the costs of PASC implementation and the cost of length of stays in hospitals, would be regarded to be adequate also for the cost-benefit analysis (Healey et al, 2022). The implementation variables include cost for time spent on implementation meetings with managers and staff, staff salaries, printing of checklists, mail costs, and digital distribution of the PASC checklist costs. Further, the variables also include costs for the patients due to actions taken after using the PASC checklist, like going to their general practitioner, dentist, nutritional diets (risks of malnutrition), and other relevant actions caused by the checklist intervention. The patient data is based on the clinical trial data and a patient survey (PASC health economic impact survey – “PASC HEI”) forwarded to a random sample drawn from within the trial. An adequate sample was calculated to 50 respondents from each cluster,

in each arm, 700 in all with a response rate at 50% (see sample calculations for the HLQ and EQ-5D-3L).

Statistical analysis plan of the PASC-Health Economic Impact data

Descriptive analysis with frequencies, percentages, mean scores, standard deviations will be applied for the patient characteristics, both for the PASC-HEI survey and for the economic evaluation of the trial. To investigate the PASC intervention impact on the health economic survey, a chi-squared test, or an independent samples t-test (ANOVA) will be used as appropriate to test for any differences between the trial arms. If there are significant variation in patients' characteristics between the two arms, a linear regression model (General Linear Model) will be applied to adjust for it and to compare effects. Analysis will be performed in SPSS 29.0 (IBM Corp, Armonk, NY) and a two-sided P value at 0.05 will be considered statistically significant.

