d. Effect size measured by the root-mean-square standardized effect.

Statistical analysis

Descriptive statistics (i.e. frequencies, percentages, mean, standard deviations) will be used to assess responding patients' characteristics, clinical variables, and surgical specialties (i.e. comorbidity, type of anesthesia or surgery, length of surgery) and EQ-5D-3L dimensions. To investigate the PASC intervention effect on EQ-5D-3L, a chi-squared test will be used to test any differences on patient characteristics between the trial arms. General Linear model with analysis of covariance will be used to investigate mean score difference between control and intervention arms. If there are significant variations in patients' characteristics and clinical variables between the two arms adjustments for these differences will be applied in the regression model to compare effects across the domains (Jansson, 2011). All analysis will be performed in SPSS 29.0 (IBM Corp, Armonk, NY) and a two-sided P value at 0.05 will be considered statistically significant.

The validity and reliability of the EQ-5D-3L will be investigated. The internal consistency will be measured by using Cronbach's alpha (scores between 0 and 1, preferably >0.7) and Pearsons' correlation or Spearman's rho as appropriate. Psychometric evaluation will be performed by measuring the hypothesized structure model of the EQ-5D-3L with fit indicators as χ^2 , CFI, TLI, and RMSEA (Bollen 1989, Kline 2011). The analysis will be performed in IBM SPSS version 29 and IBM SPSS AMOS version 26.

According to Kline (2011, p. 225) the sample size required to perform Structured Equational Modelling (SEM) usually requires 3-400 cases for models when degrees of freedom are <10. With higher degrees of freedom, i.e. > 20, a smaller number of cases is required for a minimum power of 0.80. However, the sample size should never be less than 100 in any event (Kline, 2011). The degrees of freedom within EQ-5D-3L, including 7 surgical clusters are anticipated to exceed this number on degrees of freedom. Accordingly, in all, more than 200 cases (respondents) are sufficient sample for conducting SEM (confirmatory factor analysis) with the EQ-5D-3L data. Missing data will be managed by creating 200 imputed datasets and the imputation model included all variables that to be included in adjusted regression model.

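### Knife-time, measured after PASC has begun to act, is a candidate adjustment variable in plan a), and plan e) can adjust for it because it differs between arms

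*SAP*

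**What the plan says.** **Plan a), Statistical analyses.** The primary model is a logistic regression with the control period as reference and a random intercept for hospital. For time trends, "we will include calendar month as a continuous (linear or nonlinear) term in all models". The next sentence reads "Additional adjustment would be required if selection bias is present". A list follows, kept apart from the outcome variables. It opens "Variables are gender (0/1), age (in years), comorbidity (ASA-classification 1-5), type of anesthesia (general, spinal/regional, or combination" and continues "type of surgery (nominal scores), length of surgery (knife-time in minutes/hours), type of hospital (nominal scores), and month of surgery (1-27". No sentence says which listed variables enter which model, or that a covariate must be fixed before PASC is handed out.

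**Plan a), Non-response and selection bias.** With about 50% participation expected, the SAP holds that "regression adjustment for difference in patient characteristics would probably be sufficient to adjust for selection bias".

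**Plan e), Statistical analysis.** Comorbidity, type of anaesthesia or surgery, and length of surgery are given as examples when characteristics and clinical variables are described. Then: "If there are significant variations in patients' characteristics and clinical variables between the two arms adjustments for these differences will be applied".

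**Plan b).** A logistic model will "adjust for any variations in characteristics or clinical variables between control and intervention steps". The clinical variables are not named.

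**When PASC acts.** The trial title in the SAP's introduction has the checklists used before, during and after surgery. The overview of part b) places patients' self-screening for malnutrition before surgery. Plan d) counts "costs for the patients due to actions taken after using the PASC checklist, like going to their general practitioner, dentist, nutritional diets".

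**The concern.** Plan a)'s primary hypothesis is the total effect of PASC on complications up to 30 days. A covariate that PASC can change does not belong in the main model for that effect, because holding it constant removes whatever part of the effect runs through it. Knife-time is open to three problems:

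- **Mediation.** Better-prepared patients may have shorter operations, which may lead to fewer complications.
- **Reverse causation.** Plan a) counts bleeding as a complication, and a bleed during surgery can lengthen the operation. Knife-time is then partly a result of the outcome.
- **Shared causes.** If an unmeasured patient factor drives both knife-time and complications, conditioning on knife-time can add bias once PASC also affects it.

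The rule in plan e) sharpens this. A between-arm difference in knife-time is what one would see if PASC had changed it, and that difference is what calls the adjustment in.

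**Working it through.** The SAP states no figure on this point. The check is therefore of timing and purpose first, then of size under stated assumptions.

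**1. When each listed variable is fixed, as far as the SAP says**

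| Variable | Timing |
|---|---|
| Age, gender | before PASC |
| ASA class | labelled comorbidity; time of scoring not stated |
| Type of anaesthesia | time of decision not stated |
| Type of surgery | planned or performed not stated |
| Length of surgery | during the operation, so after PASC has begun |
| Hospital, month | site and calendar time |

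Only length of surgery is post-intervention on the face of the document.

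**2. Does knife-time serve the stated purpose?** Adjustment is meant to correct differences in patient characteristics caused by selective participation. Participation is decided before the operation, so knife-time cannot itself be a reason for it. At most it stands in for planned complexity.

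**3. Size for a binary outcome (all strengths assumed).** Let A = 1 under PASC, U be an unmeasured patient factor, and L be knife-time in SD units:

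- L = −a·A + 0.4·U + error, with error variance 1 − 0.16 = 0.84
- logit P(complication) = −1.8 − 0.3·A + g·L + h·U

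Logistic models with and without L were fitted to 1,000,000 simulated patients per scenario, ignoring clusters and calendar time. Share removed = 1 − ln(OR with L)/ln(OR without L). Each pair of rows gives the extremes over g = 0.2 or 0.4 and h = 0 or 0.5.

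| a (SD) | g | h | OR without L | OR with L | Share removed |
|---|---|---|---|---|---|
| 0 | 0.2 | 0 | 0.739 | 0.738 | −0.6% |
| 0 | 0.4 | 0.5 | 0.767 | 0.758 | −4.5% |
| 0.1 | 0.2 | 0 | 0.728 | 0.741 | 5.7% |
| 0.1 | 0.4 | 0.5 | 0.727 | 0.761 | 14.4% |
| 0.2 | 0.2 | 0 | 0.722 | 0.750 | 11.7% |
| 0.2 | 0.4 | 0.5 | 0.708 | 0.781 | 28.7% |
| 0.3 | 0.2 | 0 | 0.702 | 0.745 | 16.7% |
| 0.3 | 0.4 | 0.5 | 0.680 | 0.796 | 40.9% |

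Check of one row: 1 − ln 0.750/ln 0.722 = 1 − 0.2877/0.3257 = 11.7%.

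The direct effect is −0.3 in every row. With g = 0.4 and h = 0.5, the adjusted odds ratio still drifts from 0.758 (a = 0) to 0.781 (a = 0.2) and 0.796 (a = 0.3). That drift is bias from the shared cause U, on top of mediation.

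**4. Two other assumed mechanisms**

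- PASC shortens surgery by 10 minutes and each hour multiplies the odds by 1.5: the OR goes from 0.595 to 0.633, and 1 − 0.457/0.519 = 12% is lost. By hand, the part running through knife-time is (10/60)·ln 1.5 = 0.068, and 0.068/0.519 = 13%, in line.
- PASC acts mainly on intra-operative events that add 60 minutes: the OR goes from 0.648 to 0.670, and 1 − 0.4005/0.4339 = 8% is lost.

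**5. What a loss would mean for power.** The design effect is 15% against 10%, so OR = (0.10/0.90)/(0.15/0.85) = 0.63. The stepped-wedge diagram is not available, so the rollout is assumed: seven even steps, 7 wards × 20 months × 38 patients = 5320, ICC 0.05, two-sided alpha 0.05. Hussey-Hughes power is 0.90. With 10% of the log odds ratio lost (OR 0.63^0.9 = 0.66) it is 0.84, and with 25% lost (OR 0.63^0.75 = 0.71) it is 0.70. With seven steps in months 7-13 instead, the three values are 0.69, 0.61 and 0.47.

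**6. The trigger in plan e).** With the anticipated 125 control and 200 intervention respondents, the standard error of a difference in knife-time is √(1/125 + 1/200) = 0.114 SD. Significance at 0.05 needs an observed difference of about 1.96 × 0.114 = 0.22 SD (two-sample comparison, clustering ignored). The adjustment thus comes in only when the observed difference is already sizeable, whether from chance, case mix or PASC. EQ-5D-3L is analysed by a linear model, so the percentages above do not carry over. There, the part removed is the PASC effect on knife-time times the slope of EQ-5D-3L on knife-time. The documents give neither.

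**The case against.** **Plan a) does not commit to this adjustment.** It fixes only period, hospital intercept and calendar month, makes anything further conditional on selection bias, and assigns no listed variable to a model. This stands, so knife-time in plan a) is a candidate covariate only. It remains a live candidate, because the SAP expects about 50% participation, relies on regression adjustment to deal with it, and supplies no other list.

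**A reader might infer that ASA class and anaesthesia type are equally post-intervention.** The documents do not support that. ASA is labelled comorbidity, nothing shows that PASC changes it, and it is the only comorbidity measure listed in plan a). Dropping it would weaken the defence against the selection that the SAP fears. When anaesthesia type is decided is not stated, so that is a query about timing.

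**A reader might also infer that plan b) carries the same rule as plan e).** It does not: it names no clinical variables and sets no significance condition. It only leaves room for the same problem.

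**Knife-time can stand in for surgical complexity**, which might relate to both participation and outcome. This is fair, and it is a reason to keep knife-time in a sensitivity model.

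**The loss may be nil.** This also stands. If PASC leaves knife-time unchanged, adjustment moves the log odds ratio by 0.6-4.5%, slightly away from no effect.

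**Conclusion.** The point holds as a risk that the SAP leaves open. Length of surgery is measured after PASC has begun to act, is listed in plan a) without restriction, and under plan e) can be adjusted for because it differs between arms.

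The documents do not show that any effect will be adjusted away. That needs PASC or the complication to change knife-time, and no figure in the SAP bears on it. Under the assumed inputs for complications the loss runs from nil to 6-14% of the log odds ratio for a 0.1 SD shortening, 12-29% for 0.2 SD and 17-41% for 0.3 SD. The upper ends need an unmeasured factor behind both knife-time and complications. No size can be given for EQ-5D-3L.

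The point should be corrected because the remedy is cheap and the stated purpose of adjustment gives knife-time no place in the main model.

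**What to change.** - In plans a) and e), name the main-model covariates and limit them to values fixed before PASC is handed out: age, sex, comorbidity (ASA), planned procedure type, hospital/ward and calendar time.
- Keep ASA as the comorbidity measure and state when it is recorded. State when anaesthesia type is decided.
- Move knife-time, and anaesthesia type if it is decided after PASC, to a labelled sensitivity model.
- Remove the rule that a between-arm difference in these variables triggers adjustment.
- In plan b), apply the same restriction to the unnamed clinical variables.

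This is a change of wording only. If analyses have already been run, report the models with and without knife-time side by side. The cost is slightly less explained variance, and some loss of knife-time as a proxy for surgical complexity in the main model.

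### Plan a) reads as analysing PASC participants only, and later outcome measurement does not make covariate regression sufficient against self-selection

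*SAP*

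**What the plan says.** All references are to plan a) of the SAP.

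- **Non-response and selection bias.** Preliminary data put participation at 50%. In the plan's example, "the risk of complication in complete data with no self-selection would be 15% and 10% for the control and intervention periods, respectively". It continues: "With 50% non-response (and strong selection on characteristics) in the intervention period", the risk seen could fall to 5%. The plan accepts that selection could then account for a large apparent benefit. It argues that, since the outcome comes after the intervention, only differences in patient characteristics matter, and that "regression adjustment for difference in patient characteristics would probably be sufficient to adjust for selection bias".
- **Protocol deviation and intention to treat (ITT).** For incomplete questionnaires, cancelled operations and similar violations, "we will still include subjects as if they had been treated (intention to treat analyses". The same paragraph warns that excluding violators could cause serious bias beyond the reach of adjusted regression.
- **Statistical analyses.** Descriptively, "characteristics for participants and the source population will be compared for each participating wards". Further adjustment is foreseen if selection bias is present, with no criterion for deciding that it is. The listed variables are gender, age, ASA class, anaesthesia, type and length of surgery, type of hospital and month.
- **Hypothesis.** Complications are ICD-10 codes taken from medical records.

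**The concern.** Measuring the outcome later rules out the outcome influencing participation. It does nothing to balance who enters the intervention-period data. If patients who choose to use a checklist differ in prognosis from control-period patients, the comparison is biased unless the model contains everything that drives both participation and complications. The plan a) list contains neither education nor health literacy. The SAP treats both as relevant elsewhere: the health literacy plan names educational level and societal status as patient characteristics, and health literacy itself is measured only in a survey sample of 50 patients per cluster and arm.

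The two neighbouring paragraphs also pull against each other. Excluding protocol violators is said to cause bias that adjusted regression cannot repair, yet adjusted regression is trusted for the loss of about half the patients through non-participation.

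At stake is the primary result. Randomisation acts on wards and periods, and a comparison of all control-period patients with self-selected intervention-period patients no longer has that protection. No planned analysis can separate a PASC effect from selection.

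**Working it through.** **1. Inputs.** Effect sought 15% to 10%, design 7 wards x 20 months x 38 patients, ICC 0.05, type I error 0.05, type II error 0.20 (Statistical power). Participation 50%; example risks 15%, 10% and 5% (Non-response and selection bias). Sidedness is not stated for plan a); two-sided is assumed.

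**2. The plan's figures.** 7 x 20 x 38 = 5320, as stated. For the example, overall risk = 0.5 x participant risk + 0.5 x non-participant risk. With 10% overall and 5% in participants, non-participants are at (0.10 - 0.5 x 0.05)/0.5 = 15%. The example is coherent, and it gives 5% only if the non-responding half is left out.

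**3. Size of the bias in the example.** 10% - 5% = 5 points. The effect sought is 15% - 10% = 5 points. The apparent effect doubles to 10 points.

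**4. Milder selection.** Let r be the participant to non-participant risk ratio, with overall risk 10% and half taking part. Participant risk = r x 0.10/(0.5 + 0.5r).

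| r | Participant risk | Bias (points) |
|---|---|---|
| 0.8 | 8.9% | 1.1 |
| 0.67 | 8.0% | 2.0 |
| 0.5 | 6.7% | 3.3 |
| 0.33 (plan's example) | 5.0% | 5.0 |

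**5. If control-period patients are selected alike.** With r = 1/3 in control months too, participants there are at (1/3) x 0.15/(0.5 + 0.5/3) = 7.5%. Then 5%/7.5% = 0.67, the same as 10%/15%, so the risk ratio is no longer distorted.

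**6. False positives if PASC has no effect (scenario).** Strong selection is carried over to a 15% overall risk in two ways.
- Additive: 5 spurious points. Removing half (three quarters) leaves 2.5 (1.25).
- Constant odds ratio: (0.05/0.95)/(0.15/0.85) = 0.298, which gives 7.8% in participants, or 7.2 spurious points. Removing half (three quarters) of the log odds ratio gives 11.2% (13.1%), leaving 3.8 (1.9) points.

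The standard error (SE) is from the Hussey-Hughes stepped-wedge variance. The roll-out diagram is not shown, so an even roll-out is assumed (wards crossing after months 2, 5, 8, 10, 12, 15 and 18). At 15% versus 10% the SE is 1.54 points, used for the odds-ratio rows; the additive rows use 1.61 and 1.64, recalculated at their mean risk. The chance of a significant result favouring PASC is Φ(bias/SE - 1.96), against a nominal 2.5%.

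| Selection removed | Additive | Constant odds ratio |
|---|---|---|
| Half | Φ(2.5/1.61 - 1.96) = 34% | Φ(3.8/1.54 - 1.96) = 69% |
| Three quarters | Φ(1.25/1.64 - 1.96) = 12% | Φ(1.9/1.54 - 1.96) = 24% |

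With the SE implied by the stated 80% power, 5/(1.96 + 0.84) = 1.79 points, the rows become about 29% to 56% and 10% to 19%.

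**7. Power of an all-eligible analysis.** At 50% uptake, with a 5-point effect in participants only, the contrast is 15% versus 12.5%, or 2.5 points. On the same assumed roll-out:

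| Eligible per ward-month | SE (points) | Power |
|---|---|---|
| 38 in all months (38 counts all eligible) | 1.61 | 0.34 |
| 38 in control, 76 in intervention months | 1.35 | 0.46 |
| 76 in all months (38 counts participants) | 1.14 | 0.59 |

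**The case against.** The strongest reply is that the SAP never says non-participants are left out. The 50% is a preliminary rate, the example is hypothetical, the ITT paragraph ends with a catch-all for other deviations, and enrolment rules usually sit in a protocol that is not at hand. This stands in part: the participant-only set is an inference. It is a firm one, because the example needs it and the selection section would have little purpose if every eligible patient were analysed.

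Second, the plan does recognise the problem. It will compare participants with the source population and foresees further adjustment, and ASA class carries some information on frailty. That also stands. It does not rescue the sufficiency claim, because such comparisons see only recorded characteristics.

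Third, selection may operate in control months too. Then the bias shrinks, as step 5 shows. The plan's example puts non-response in the intervention period only, and nothing in the SAP provides for equal recruitment in both.

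A reader might infer that the primary analysis carries a false-positive rate near 70%. The documents do not support that. The figure needs strong selection in intervention months only, a constant odds ratio carried to the null, covariates that remove just half of it, and an assumed roll-out.

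**Conclusion.** The concern holds in this form: plan a) reads as an analysis of participants, and its argument that regression will probably suffice is unsound because prospective outcome measurement does not deal with unmeasured differences in who takes part. The possible bias equals the 5-point target in the plan's own strong-selection example and is about 1.1 to 3.3 points under milder selection, before any adjustment. It is smaller if control-period patients are self-selected in the same way. Residual false-positive rates of 12% to 24% (three quarters removed) or 34% to 69% (half removed) are illustrations under the assumptions in step 6, not predictions.

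Two stronger readings should be avoided. The SAP does not state that only participants are analysed. Nor does it show that selection in this trial is as strong as in its example; it says only that it could be.

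**What to change.** 1. Add a supportive ward-period intention-to-treat analysis of all eligible operated patients in each ward-month, regardless of participation, using the ICD-10 record outcomes. Ward-month counts are enough. Report its estimate and confidence interval beside the participant analysis, and interpret it in light of dilution by non-participants.
2. Remove the sufficiency statement and its prospective-design justification. State instead that the adjusted analysis assumes all characteristics related to both participation and outcome are measured.
3. Call the present set *all participants*, or, if non-participants are meant to be included, say so.

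Inverse-probability-of-participation weighting is optional. It rests on the same measured characteristics and does not address unmeasured selection.

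The cost is one further record extract, subject to any approval needed, one added model and a few changed sentences. With power of 0.34 to 0.59 for the diluted effect, the added analysis would often miss a real benefit, so a non-significant result should not by itself veto the participant result.
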